Individuals interested in the study will receive a brief telephone screening to determine if they may be eligible to participate. They will then be scheduled for an initial assessment session, consisting of an informed consent procedure, followed by completion of medical history, physical exam, self-report questionnaires, and semi-structured interviews to determine study eligibility. If volunteers complete the informed consent process and are eligible for participation, they will be enrolled in the study. A comprehensive battery of instruments will be administered to characterize participants' smoking, stressor exposure history (past and current), and general psychiatric functioning (see Instruments/Measures, Section C3g.). The research team will use several methods of contact to keep in touch with participants. We will ask them to provide us with phone numbers, e-mail

addresses, current home and work addresses, and contact information of family and friends who may know how best to reach them. We will also have a Facebook account that we may use to contact participants. The research team will only use private messages to contact participants through Facebook

We considered incorporating luteinizing hormone home testing kits to randomize female participants to start study procedures at the outset of the follicular or luteal menstrual cycle phase, but opted not to for multiple reasons. First, we noted in our initial SCOR study that the associated lag in initiation of study procedures for some women was associated with relatively high dropout rates. Additionally, the proposed study will enroll both men and women and we wanted to avoid using any menstrual phasing procedures that would result in substantially different treatment of male and female participants (i.e., long delays before the occurrence of study procedures for some females but no delays for other females and all males). Second, we noted in our subsequent SCOR study that enrolling a similarly sized sample of women resulted in an even distribution of enrollees across the menstrual cycle (while also resulting in improved participant retention rates). We also felt it important to progress from a “follicular versus luteal” phase approach to a continuous measurement approach involving the direct assessment of hormone levels. Therefore, we elected to use a participant enrollment approach that will allow women to enroll at any time/stage of the menstrual cycle.

C3d. Training Procedures.

Enrolled participants will return for a training visit, during which they will gain mastery of saliva sample collection and storage, personal digital assistant (PDA; iPhone) operation, and CREMA procedures.

C3e. Natural Environment Procedures.

CREMA Assessment. Participants will carry a PDA for two weeks (Days 1-14). They will be instructed to keep the PDA with them at all times. Auditory alarms will alert participants to complete four, randomly scheduled cue-reactivity/CREMA sessions per day (session duration = 3-4 min.). Alarms will be distributed over a 12-hour period, divided into four, 3-hr blocks with a minimum time of 30 minutes between alarms/CREMA sessions. Each CREMA session will contain two trials and each trial will consist of one picture cue presentation. There will be three types of picture cues that differ based on content: stressful (e.g., stress-inducing images from the standardized International Affective Picture System [IAPS; Libkuman et al., 2007; Rehme et al., 2009]), smoking (e.g., lit cigarettes, people smoking, etc.) and neutral (e.g., pencils, scissors, etc.). Thus, each of the four daily CREMA sessions will contain two picture cues from one or a combination of these three categories.

At the start of each CREMA session, participants will be asked to finish their cigarette if they were smoking, then provide craving and mood ratings, and answer questions about distractibility, etc. (see Section C3g. Instruments/Measures). Next, a photograph will be presented and the participant will be instructed to look at it carefully. Each picture cue will appear only once during the study. An alarm will sound at the end of each trial, after which participants will complete a post-cue assessment consisting of the Craving Questionnaire, mood items, and ratings of how carefully they looked at the photograph and their distraction level during each trial. CREMA sessions will present the pictures for 10 seconds.

Participants will be prompted for four CREMA sessions per day on Days 1-14, and will thus complete a maximum of 56 CREMA sessions. To encourage CREMA session completion, participants will be compensated \$1.25 for each completed session (see Participant Compensation, Section C3h). Previous studies employing this incentive strategy have reported 90% CREMA completion rates (Gass, et al., 2011; Warthen & [name], 2009a; Wray, et al., in press).

Saliva Sample Collection. Participants will, via established procedures reviewed during the training visit, collect saliva samples a half hour after awakening. Samples will be dispensed into containers supplied by study staff, and stored in participants' home freezers until bringing the samples to a subsequent study visit. The laboratory will analyze samples for levels of estradiol & progesterone (females only) and testosterone (males only). These daily home collection and storage procedures have been used in numerous previous studies with excellent participant adherence and sample quality (Edler, et al., 2007; Klump, et al., 2008).

C3f. Laboratory Procedures.

An overview of the laboratory session procedures is presented in the Laboratory Procedure Timeline table. Participants will receive the following instructions to prepare for their laboratory session: they are to 1) abstain from smoking for 12 hours; generally, this will mean not smoking overnight before the laboratory session, 2) abstain from alcohol/other drug use for a minimum of two days prior to the laboratory session, 3) perform saliva collection the morning of the laboratory session and bring it, as well as the samples collected during the previous week, to the appointment, and 4) arrive at MUSC's Clinical Neurosciences Division office between 9:00 and 9:30

AM the day of their scheduled laboratory session. Upon arrival at the office, participants will provide research staff with the saliva samples they collected over the previous 8 days; in the event that a participant fails to collect a saliva sample the morning of the laboratory session, (s)he will be requested by research staff to provide a sample on site. Smoking abstinence will be confirmed via carbon monoxide assessment and abstinence from alcohol/other drug use will be assessed via breathalyzer and urine drug screen (UDS). Participants who fail any of the abstinence assessments will have their laboratory session re-scheduled at the earliest possible date. Individuals who must reschedule their laboratory session will be asked to continue to collect saliva samples daily upon awakening until the day of their laboratory session. Next, sensors for the measurement of heart rate and skin conductance will be affixed to the participant and a blood pressure cuff fastened to the non-dominant arm. Participants will complete baseline assessments (salivary cortisol, craving, stress, mood, etc.) and then receive a lunch snack. Participants will sit quietly for approximately 20-30 minutes after finishing their snack and then will receive nasal administration of either oxytocin or placebo (described in more detail below) at 12:00 noon. Approximately 30 minutes following medication administration, a second set of baseline measures will be obtained, after which the participant will sit comfortably until the Trier Social Stress Test/TSST (Kirschbaum, Pirke, & Hellhammer, 1993) begins.

The TSST procedure is widely recognized as the gold standard for evoking stress response in the laboratory (Dickerson & Kemeny, 2004). It begins when the participant is told that (s)he will soon have to perform both a speech and arithmetic task in front of an audience. They are told that the topic of the speech is why (s)he should be hired for a particular job (the participant's "dream job"). The participant will deliver the speech as though speaking to a group of hiring managers. The experimenter then tells the participant that (s)he has 5 min to prepare the speech, and starts the countdown clock (placed in view of the participant). The experimenter leaves the room to allow the participant to prepare. Five minutes later, three individuals unfamiliar to the participant (the audience) enter the room and are seated; the participant is instructed by one audience member (the spokesperson) to stand and begin his/her prepared speech (without notes). The speech is delivered for 5 min; if the participant pauses, (s)he is instructed by the spokesperson to continue. At the end of the speech task, the participant is instructed to serially subtract 13 from 1,022 as quickly and accurately as possible. The mental math recitation continues for 5 min, and at its conclusion, the spokesperson instructs the participant to stop and be seated, and the audience leaves the room. The total time for the TSST procedure is approximately 15 min.

Laboratory Procedure Timeline

TIME	PROCEDURE(S)	MEASUREMENT(S)		
10-10:55 AM	General Assessment & Preparation	CO Assessment; Breathalyzer; UDS; Saliva collection (if not done at home); NWSC; STAI, Mood Form; DDT.		
11:00-11:30 AM	Placement of HR & SC sensors & BP cuff; Baseline 1 Measurements; Snack.	CQ; CREMA Mood & Stress Assessment; NWSC; HR, SC & BP; Cortisol.		
12:00 Noon	Intranasal Administration of Oxytocin or Placebo			
12:30 PM	Baseline 2 Measurements	CQ; CREMA Mood & Stress Assessment; NWSC; HR, SC & BP; Cortisol		
12:45-1:00 PM	Trier Social Stressor Task (TSST)			
1:00 PM	Immediate post-TSST assessment; SRT begins.	CQ; CREMA Mood & Stress Assessment; NWSC; HR, SC & BP; Cortisol; DDT		
1:20 PM	20-minute, post-TSST assessment	*Cortisol & subjective stress (verbal report) will be assessed 20, 40 & 60 min. post-TSST.	*CQ, CREMA Mood & Stress Assessment, NWSC, HR, SC & BP will be assessed when each participant ends SRT and during ASP at 30 and 60 min.	
1:40 PM	40-minute, post-TSST assessment			
1:50 PM	Maximum duration of SRT reached. Latest time that ASP begins.			
2:00 PM	60-minute, post-TSST assessment			
2:50 PM	ASP Ends.			
2:50-3:20 PM	Sensors removed; participant debriefing and compensation.			

Table Key: UDS=Urine Drug Screen; CO= Carbon Monoxide; NWSC=Nicotine Withdrawal Symptom Checklist; STAI=State-Trait Anxiety Inventory; DDT = Delay Discounting Task; CQ=Craving Questionnaire; CREMA=Cue Reactivity Ecological Momentary Assessment; HR=Heart Rate; SC=Skin Conductance; BP=Blood Pressure; SRT=Smoking Resistance Task; ASP=Ad libitum Smoking Period.

The participant will then complete the Smoking Resistance Task (SRT), which is a empirically validated laboratory model of smoking lapse behavior (McKee, 2009; McKee, Krishnan-Sarin, Shi, Mase, & O'Malley, 2006; McKee, et al., 2011). The task involves testing the ability of overnight abstinent smokers to resist smoking in a situation where they are free to smoke but continued abstinence is reinforced with money. In the present case, a participant's preferred brand of cigarettes and a lighter will be presented on a tray. The experimenter will explain that the participant may begin smoking at any time, but the participant will be eligible to earn \$1.50 for every 5 minutes the participant is able to "resist" smoking (up to a total of 50 minutes or \$15). Once (s)he elects to smoke, the participant will begin the Ad libitum Smoking Period (ASP), in which (s)he is permitted to smoke as much as desired over the next hour in the laboratory. Topographical features of smoking behavior will be measured using the CReSS Pocket (CReSS, Borgwaldt KC, Inc., Richmond, VA), a self-contained, battery-operated device. In addition, the experimenter will record the number of cigarettes smoked.

Oxytocin/Placebo Administration: As noted above, participants will be administered 40 IUs of oxytocin or matching placebo nasal spray at approximately 12:00 noon. This dose and timing of administration was selected based on previous studies that have used similar doses of oxytocin (Ditzen et al., 2009; Heinrichs, et al., 2003; Macdonald et al., 2011), as well as our own previous pilot work (see Preliminary Data). Intranasal oxytocin and matching placebo will be compounded by MUSC Investigational Drug Service (IDS). The concentration of oxytocin will be 40 IUs/ml. Randomization will be done by the MUSC Investigational Drug Service, who will keep a record of the blind and be available should unblinding be necessary.

C3g. Instruments/Measures.

The diagnostic instruments/assessments employed in this investigation are widely cited, standardized instruments that have strong psychometric properties. This project has several instruments in common with Projects 1 in an attempt to foster assessment synergy between clinical projects. A brief description of each measure is as follows (where possible, instruments are grouped according to purpose and/or timing of use):

i. **Initial General/Diagnostic Assessments:** Demographic and Medical Information Assessment Form will be used to assess standard demographic information at baseline (using the NIH race/ethnicity categories) and medical history; Mini-International Neuropsychiatric Interview or MINI (Sheehan et al., 2003; Sheehan et al., 1998) will be used to assess general psychiatric functioning and DSM-IV diagnostic status, including alcohol and other drug abuse and dependence; Structured Clinical Interview for DSM-IV (SCID-I/P) is a structured diagnostic interview that assesses each of the criteria for DSM-IV diagnoses. The substance use disorder modules from the SCID are used as an alternative for these modules in the MINI. The SCID has proven to have excellent inter-rater and test-retest reliability (First et al., 2002); Daily Hassles Scale (DeLongis, Folkman, & Lazarus, 1988) consists of a list of irritating, frustrating or distressing events that characterize everyday interactions with the environment (participants rate both frequency and intensity of events for the past month); Adverse Childhood Experiences Questionnaire and ACE Brief (ACE; Felitti et al., 1998) assess childhood maltreatment and exposure to household dysfunction (employing the ACE will allow for potential cross-SCOR collaborations as it also being employed by the UCLA SCOR); Toronto Alexithymia Scale (TAS-20, Bagby, Parker & Taylor, 1994) is a scale which measures alexithymia, a condition in which people have trouble identifying and describing feelings. Items are rated using a 5-point Likert scale whereby 1 = strongly disagree and 5 = strongly agree. Both the original, 1985 version and the revised, 1992 version will be administered at the assessment visit; Modified Cigarette Evaluation Questionnaire (mCEQ, Rose, Behm, & Westman, 1998; Brauer, Behm, Westman, Perkins, & Rose, 2001) is a 12-item questionnaire assessing the reinforcing effects of smoking and contains 5 subscales (smoking satisfaction, psychological reward, enjoyment of respiratory tract sensations, craving relief, aversion) that will be given at screening, Day 7, and during the laboratory session post-cigarette during the ASP; The Distress Tolerance Scale (DTS, Simmons & Gaher, 2005) is a validated self-report which measures tolerance, appraisal, absorption, and regulation of emotional distress; Timeline Follow-Back (TLFB; Sobell & Sobell, 1992) is a calendar-based instrument with specific probes to obtain detailed information about substance use (including smoking) that will be used to assess smoking and other substance use in the three months prior to study involvement; Smoking History Form will be used to assess current smoking patterns, smoking environment, and previous smoking quit history; Fagerström Test for Nicotine Dependence (FTND; Heatherton, Kozlowski, Frecker, & Fagerstrom, 1991) will be used to assess degree of nicotine dependence; Menstrual History Diary

will be used to assess the timing of the menstrual cycle of female participants for the 90-days prior to study entry and to track their cycle during study participation. The Pittsburg Sleep Quality Index will be used to assess sleep patterns (Buysse, et al., 1989). Anxiety and depression symptoms will be assessed through The Quick Inventory of Depressive Symptoms (Rush, et al., 2003) and from the PROMIS® item bank (US DHHS). Daily stress will be obtained using the 10-item Perceived Stress Scale (PSS; Cohen et al., 1983). The Life Events Occurrence Scale (Maciejewski, et al.) will be used to inventory adult trauma. A brief survey from the National Health and Nutrition Examination Survey (CDC, 2000) will be used to rate quality of life. A body map will be used to rate areas of pain (Cleeland et al., 1989).

Genetic Testing

Consenting participants will have blood drawn for genetic testing. This will typically occur during the assessment unless circumstances do not permit. We plan to examine genes associated with stress and cigarette smoking. Our group has previously collaborated with [name] at Virginia Commonwealth University (VCU), whose research group is actively investigating genetic variations associated with stress and nicotine use. Samples will be collected and stored at the MUSC Clinical Neurobiology Lab and periodically shipped to [name] Laboratory at VCU for analysis.

ii. Daily (Longitudinal) Assessments: Craving Questionnaire/CQ (Carter & [name], 2001) is a 4-item self-report questionnaire that assesses urge to smoke in all CREMA sessions. CREMA Stress/Mood Assessment (Warthen & [name], 2009a; Wray, et al., in press) will assess stress, negative mood ("I am stressed, depressed, angry, worried, or frustrated") and positive mood ("I am happy, joyful, or pleased") during CREMA sessions. CREMA validity scales (Warthen & [name], 2009a; Wray, et al., in press) assess distractibility and attentiveness during CREMA sessions using 5-point rating scales (strong disagreement=1; strong agreement=5). As noted above, saliva samples will be collected on a daily basis in order to determine levels of estradiol (females only), progesterone (females only) and testosterone (males only). Qualified laboratory technicians at MUSC's Clinical and Translational Research Center (CTRC) will perform all assays using commercially available immunoassay kits provided by Salimetrics™.

iii. Laboratory Session Assessments: As above, the Craving Questionnaire (CQ) and the CREMA Mood/Stress Assessment will be used to assess craving/urge to smoke and stress/mood at multiple time points during the laboratory session, respectively; State-Trait Anxiety Inventory (STAI; Spielberger, Gorsuch, Lushene, Vagg, & Jacobs, 1983) will be administered at the beginning of the laboratory session to assess state anxiety levels; Mood Form is a 9-item form (Diener & Emmons, 1984) that will be administered at the beginning of the laboratory session and will provide an immediate, corroborative assessment of current positive and negative mood states; Nicotine Withdrawal Symptom Checklist/NWSC (Hughes, Hatsukami, & Skoog, 1986) will be used to assess several withdrawal symptoms (i.e., craving, irritability/anger, anxiety/tension, difficulty concentrating, restlessness, etc.) from 0 to 4 (0 = not present, 4 = severe) at the laboratory visit; Delay Discounting Task is a 27 item form that will be measured before and after TSST and provides estimates of impulsivity and the degree to which participants discount future rewards; Heart rate and skin conductance (indices of physiological arousal) will be measured repeatedly over the course of the laboratory session. Heart rate (HR) will be collected via two electrodes along the bottom of the participant's ribcage, rather than on the participant's forearm, to minimize movement artifacts while skin conductance (SC) will be recorded using Ag/AgCl electrodes attached to the second phalanx of the first and third fingers of the non-dominant hand (HR and SC signals will be amplified using the ECG 100c and GSR 100c Modules of the Biopac MP100 data acquisition system); Blood pressure (BP) will be measured repeatedly via a non-invasive arm cuff; Cortisol levels will be determined via salivary samples collected at regular time intervals over the course of the laboratory session (they will be processed at the CTRC as described ii. above); Penetration of the Blind Questionnaire will be used to assess patient's opinion regarding whether they were administered the study medication or placebo; Adverse Events (AE) form will be used to document any participant-reported adverse events, whether related or unrelated to session procedures, including intranasal oxytocin or placebo administration.

C3h. Participant Compensation.

Participants will receive \$100.00 for completing the comprehensive assessment. They will also receive \$50 for attending the training visit and each interim visit (at Day 7); to incentivize compliance with the salivary data collection procedures, participants will be paid \$5.00 per each day's useable saliva sample delivered at the

Version 12.0 (01/12/2016)

interim visit. In the interest of incentivizing attendance at the laboratory session and in recognition of the fact that this session involves exposure to a stressor and a significant time commitment, participants will be paid \$100.00. Since participants will be delivering their saliva samples (obtained over the previous week) when they attend the laboratory sessions, they will be paid an additional \$5.00 for each useable daily sample they provide. Given that the laboratory session will involve the administration of the smoking resistance task (SRT), it will be possible for participants to earn up to \$15.00 if they successfully resist smoking for the entire 50 min. resistance period. As noted above, the completion of CREMA sessions will be incentivized by paying participants \$1.25 for each session with complete data. Participant travel expenses up to \$50 are allowable on an as needed basis. Thus, maximum remuneration for study participation is \$510.

C3i. Sample Size Determination.

This study is powered to test the hypothesis that non-cigarette-deprived females will be more reactive to smoking cues than males, as measured in the natural environment of smokers via CREMA technology. However, the sample size obtained for this is adequate to test all the four hypotheses with at least 80% power. The justifications for the power calculations are as follows. A recent study (Heishman, et al., 2010) found that non-cigarette-deprived females responded to smoking cues with 10% greater craving than males (i.e., 10-unit difference on a 100-mm VAS), with this difference corresponding to an effect size of $d = 0.7$. Since the proposed design intends to assess gender differences in a non-laboratory setting, we have reduced the expected effect size by 30% to 0.50. Based on the four-item subscale of the QSU (cf., Warthen & [name], 2009b) to be used in the proposed study, a comparable detectable gender difference would be 0.45 ($sd=0.9$). Accounting for the multiple correlated measures within each participant (i.e., reactivity will be measured multiple times daily for 14 days using CREMA) through a between-observation correlation (autocorrelation) of 0.70, a sample of 96 females and 48 males is necessary to achieve 90% power (with a two sided type I error rate of 0.05) to detect the minimum relevant effect size of $d=0.50$. It is estimated that up to 20% of the participants may be lost before completion of the study.

Assuming 144 participants complete all study procedures (accounting for 20% dropout), we will also have 80% power with a type I error of 0.05 to detect a minimum effect size of $d=0.50$ between females and males in stress and craving response to the TSST and similarly between the oxytocin and placebo groups.

C3j. Data Management & Statistical Analysis.

Data Management

All paper-based assessments will be entered into SPSS databases using dual data entry methods for 20% of cases. Semi-annual database management and data integrity audits will be conducted. Hormone and cortisol data will be obtained from MUSC's CTSC in pre-formatted data files. HR and SC data will be acquired via specialized software and hardware (Biopac Systems, Inc.) interfaced with a computer. Standardized file formats will facilitate the rapid determination of summary values to be used for analysis purposes. The CREMA data will be automatically uploaded to a server on a daily basis and will be stored in a standard file format (to be determined in collaboration with [name] (Founder of Slicker Interactive & CREMA software developer). All data will be de-identified using participant ID number.

Statistical Analysis

Univariate descriptive statistics and frequency distributions will be calculated for all variables. Departures from distributional assumptions for the proposed parametric methods will be identified and appropriate transformations of the data will be applied or alternative procedures (semi/non parametric methods) will be employed. Baseline values for demographic, clinical, and other prognostic variables will be compared for imbalance across gender and treatment groups. These analyses will identify potential confounding variables to be used as covariates in subsequent analysis.

Aim 1: Hypothesis 1 - To test the overall hypothesis that females will be more reactive than males to stressful and smoking-related cues presented in the natural environment, a linear mixed effects model will be employed. The dependent variable will be craving and the primary independent variable will be gender. In the modeling process, within-subjects factors of stimulus type (active and neutral cues) and presentation order will also be included.

Hypothesis 2 - To test the hypothesis that the estradiol to progesterone ratio will be positively related to cue-elicited craving in the natural environment, salivary hormone levels and craving in response to the CREMA picture cues will be assessed over 14 days. Hormone curves do not behave in a linear fashion, but may, in the example of progesterone, behave in a quadratic fashion preceding menses and a linear fashion following

menses. Linear models may thus be inappropriate. Traditional analyses group the hormone curves based on the estimated phases of women's menstrual cycle (follicular and luteal) for the analyses. In addition to performing the data analyses using the same method, analysis will be extended to incorporate the non-linear patterns of an individual's hormone profile. This method will be based on a non-linear regression model that has two to three segments, each one of which may be either quadratic or linear (Marrie, Dawson, & Garland, 2009). The 'joint-points' at which the segments meet, which are referred to as knots, will also be treated as unknown and determined through the modeling process. After identifying the segments, regression models assessing hormone measures against the outcome (e.g., cue-elicited craving) in each segment will be assessed and the results interpreted accordingly.

Aim 2: Hypotheses 1 and 2 - To test for gender and medication (oxytocin versus placebo) effects on reactivity profiles to the TSST during the laboratory session, a linear mixed effects model in which the dependent variables of interest are craving, stress and neuroendocrine (cortisol) response, and the primary independent fixed effects are gender, treatment group, and a random subject effect will be utilized. To account for the repeated measures, a covariance pattern for the error structure (such as an AR(1)) will be considered. The primary goal of this analysis will be to determine if the response to TSST is significantly different between females and males and/or significantly different between those who received oxytocin versus placebo (main effects of gender and medication). Additionally, as a secondary analysis, the interaction between gender and medication condition will be explored.

To test the hypothesis that females will have a shorter latency to return to smoking than males, a discrete analog to the Cox proportional hazards model will be used. A complementary log-log model for interval censored survival times will be employed (Allison, 1982; Prentice & Gloeckler, 1978) that will take into account the interval nature of the time frame within which the return to smoking occurs. Also considered will be standard Cox proportional hazards models to compare time to begin smoking. Puff intensity, flow rate, and number of puffs will be assessed using a topography device as participants smoke freely for 1 hour following the smoking resistance task. Longitudinal data analytic methods will be applied to the craving, stress and cortisol data obtained during the laboratory session for all time points before and after the TSST.

Hypothesis 3 - To test the association between the estrogen to progesterone ratio and laboratory stress reactivity in women, a linear model will be developed to assess the relationship between hormones and subsequent stress reactivity. The dependent variables of interest will be the craving, stress and neuroendocrine (cortisol) response to the TSST while the independent variables will include the change in the hormone ratio over the week preceding the lab visit as well as the hormone ratio on the day of the visit. Assumptions such as linearity of the relationship between the hormones and reactivity measures, homoscedasticity, and normality of the error distribution will be assessed and variables will be transformed as necessary.

C3k. Operational Plan and Research Timetable.

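### The Aim 2 oxytocin comparison names no pre-dose covariate for craving or stress, although about 47 to 50 CREMA ratings on the same instruments and a same-day Baseline 1 will be available

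*Combined protocol and SAP*

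**What the plan says.** C3g ii states that the Craving Questionnaire (CQ) "is a 4-item self-report questionnaire that assesses urge to smoke in all CREMA sessions", and it assigns the CREMA Stress/Mood Assessment to the same sessions. C3e schedules four sessions a day on Days 1 to 14, at most 56, and cites 90% completion in earlier studies. Each session opens with craving and mood ratings before any picture is shown.

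For the laboratory session, C3g iii says that "the Craving Questionnaire (CQ) and the CREMA Mood/Stress Assessment will be used to assess craving/urge to smoke and stress/mood at multiple time points". C3f and its timeline place Baseline 1, with both forms, before the noon dose.

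For Aim 2, Hypotheses 1 and 2, C3j describes a mixed model in which "the primary independent fixed effects are gender, treatment group, and a random subject effect will be utilized". The stated goal is the main effects of gender and medication on response to the TSST. The data are those collected during the laboratory session, at all time points before and after the stressor. C3j also has a general rule under which baseline variables are compared for imbalance across gender and treatment groups, in order to find confounders to use as covariates.

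C3i assumes a "between-observation correlation (autocorrelation) of 0.70" for CREMA reactivity and says that "the sample size obtained for this is adequate to test all the four hypotheses with at least 80% power".

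**The concern.** Oxytocin versus placebo is the trial's randomised comparison, and it is made between participants. Stable differences between people in craving and stress therefore enter the standard error of the medication main effect. A random subject effect models that variance but does not remove it from a between-subject contrast. A prognostic person-level covariate would remove part of it.

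Two such covariates are already being collected before dosing on the outcome's own instruments: Baseline 1 and the CREMA ratings. The plan does link its two phases elsewhere: Aim 2 Hypothesis 3 uses the change in the hormone ratio over the week before the laboratory visit. The craving and stress ratings from the same two weeks are not carried across. The imbalance screen does not fill the gap, because in a randomised comparison the reason to adjust is prognostic strength, not observed imbalance. A covariate chosen by screening is also not prespecified.

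At stake is the width of the confidence interval for oxytocin on craving and stress. Bias is not at issue.

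**Working it through.** **Ratings before dosing.** 56 × 0.90 = 50.4. C3a puts the laboratory session on the last day of week two, whereas the Specific Aims put it after the two weeks. If only Days 1 to 13 count, 52 × 0.90 = 46.8. C3e names the CQ explicitly only for the post-cue rating. I take the pre-cue craving rating to be the CQ as well, because C3g ii assigns it to all sessions.

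**Reliability of the person mean.** With correlation 0.70 between ratings, m × 0.70 / (1 + (m − 1) × 0.70) gives 32.9/33.2 = 0.991 for m = 47 and 35/35.3 = 0.992 for m = 50. Here the 0.70 is borrowed from C3i, where it describes repeated CREMA reactivity.

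**The plan's own figure.** C3i gives 144 completers (96 women, 48 men), d = 0.50 and 80% power for the laboratory contrasts. I use "with a two sided type I error rate of 0.05", which C3i states for the primary contrast. Noncentral t power is 80.2% for 48 versus 96, which reproduces the 80% for gender. With 1:1 allocation, 72 versus 72 gives 84.6% for oxytocin (85.1% by the normal approximation), consistent with at least 80%.

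**CREMA mean as the only covariate.** Let r be its correlation with the laboratory outcome, an assumption. Residual variance is multiplied by 1 − r², the detectable d is divided by √(1 − r²), and the equivalent sample is 144/(1 − r²).

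| r | Variance removed | Power | Equivalent N |
|---|---|---|---|
| 0.2 | 4% | 86.0% | 150 |
| 0.3 | 9% | 87.8% | 158 |
| 0.4 | 16% | 90.2% | 171 |
| 0.5 | 25% | 93.1% | 192 |
| 0.6 | 36% | 96.1% | 225 |

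The lost degree of freedom is repaid once r exceeds about √(1/141) = 0.08.

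**CREMA mean added to Baseline 1.** Let b be the correlation between Baseline 1 and the outcome, and g the correlation between a person's usual daily-life level and usual laboratory level. Neither is in the documents. The CREMA mean then correlates c = g × √(b × 0.99) with both Baseline 1 and the outcome. The further proportional fall in residual variance is c²(1 − b) / [(1 − c²)(1 + b)]. For example, with b = 0.70 and g = 0.5, c² = 0.173, and 0.173 × 0.30 / (0.827 × 1.70) = 3.7%.

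| b | g | Further variance removed | Power, Baseline 1 alone | Power, both |
|---|---|---|---|---|
| 0.70 | 0.2 | 0.5% | 98.7% | 98.7% |
| 0.70 | 0.3 | 1.2% | 98.7% | 98.7% |
| 0.70 | 0.5 | 3.7% | 98.7% | 98.9% |
| 0.70 | 0.8 | 14.1% | 98.7% | 99.4% |
| 0.50 | 0.2 | 0.7% | 93.1% | 93.2% |
| 0.50 | 0.3 | 1.6% | 93.1% | 93.4% |
| 0.50 | 0.5 | 4.7% | 93.1% | 94.1% |
| 0.50 | 0.8 | 15.5% | 93.1% | 96.3% |

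For g = 0.5 to 0.8, the CREMA mean adds about 0.2 to 3 points of power beyond Baseline 1 and narrows the interval by about 2% to 8%.

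**Change from Baseline 1 as the outcome.** In this structure the CREMA mean correlates equally with both readings, so its correlation with their difference is c − c = 0 before scaling, and it gains nothing.

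**The case against.** The strongest reply is that the gain specific to the CREMA ratings may be negligible. CREMA ratings come from smokers who are not deprived and who are told to finish a cigarette first. Laboratory ratings follow 12 hours of abstinence and a social stressor. The link between them could be weak, and at g = 0.2 to 0.3 little is gained beyond Baseline 1. C3j also speaks of response to the TSST and of reactivity profiles. If that means change from Baseline 1, stable differences largely cancel. Its list is of primary fixed effects, which does not exclude further terms, and the imbalance screen could in principle admit a CREMA mean. Cortisol, also a Hypothesis 2 outcome, has no CREMA counterpart. Unadjusted power already exceeds the plan's claim.

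Most of this stands, and it limits the point to an optional improvement. It does not remove it. C3j states its target as main effects and specifies no change score. It treats Baseline 1 as an analysed time point, not as a stated covariate. An imbalance screen is not a prespecified precision adjustment.

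Three stronger readings are tempting, and the documents do not support them. A reader might infer that the plan keeps the two phases wholly apart, but Hypothesis 3 reuses the daily hormone data. A reader might credit the CREMA ratings with raising power from 84.6% to 91% to 98% (g = 0.5 to 0.8 with ratings correlated 0.70). That comparison has no baseline adjustment at all, and on the same assumptions Baseline 1 alone reaches 98.7%. A reader might also average all of Days 1 to 14. Under C3a's timing, some Day 14 ratings could follow the dose.

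**Conclusion.** The gap is real: C3j names no pre-dose covariate for craving or stress in the oxytocin comparison, although two are collected on the same instruments. It is a missed efficiency, not an error, and it creates no bias or contradiction. The comparison is adequately powered on the plan's own terms, at about 85% unadjusted for d = 0.50 with 72 per arm.

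Most of the recoverable precision could come from Baseline 1 alone. What the CREMA mean adds beyond it is uncertain: about 0.5% to 1.5% of residual variance for g = 0.2 to 0.3, about 4% to 15% for g = 0.5 to 0.8, and essentially nothing for a change-from-baseline outcome. These figures rest on assumed values of b and g, on equal correlation of the CREMA mean with Baseline 1 and the outcome, and on a single post-dose rating as outcome. The gain applies to craving and stress only. I would class this as a change the team could make.

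**What to change.** In C3j, Aim 2 Hypothesis 2, state that the craving and stress models will include two covariates, whether or not they are imbalanced between arms:

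- the Baseline 1 rating of the same outcome, which then serves as a covariate and not as one of the responses;
- the participant's mean pre-cue CREMA rating of the same outcome (CQ for craving, CREMA stress rating for stress), using only sessions completed before dosing.

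Centre the CREMA mean within gender, so that the gender effect tested in the same model is not adjusted away. For participants without CREMA data, use the within-gender mean with a missing indicator. Say also whether response to the TSST means post-dose level or change from Baseline 1, since the value of the second covariate depends on it. Settle this before unblinding.

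The cost is one or two sentences and one derived variable per outcome, with no new data, visits or participants. The CREMA term uses one degree of freedom, or two with the missing indicator, and its gain may prove small.
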